8.5.4. Safety Monitoring for Bleeding Events

Patients will be evaluated for occurrence of bleeding events continuously after the start of Study Drug treatment (Day 1) up to the end of the Follow-up Period. All bleeding events are considered AEs and reported on the AE case report form (CRF).

If an event of major bleeding (MB) or clinically relevant non-major bleeding (CRNMB) event occurs (as defined below), the Investigator or designee must notify the Medical Monitor (or designee) and the patient should be treated, as needed, immediately and closely monitored (vital signs, lab tests such as hemoglobin (Hb), hematocrit, and PLT count, additional visits, overnight stays and coagulation tests may be needed if deemed appropriate by the treating physician) throughout the Treatment and Post-Treatment Periods and an (S)AE CRF will be completed. In addition, approximately 2 mL of K2 EDTA anticoagulated blood will be collected and resulting plasma must be stored allowing for a centralized assessment of ISIS 721744 concentrations.

If a minor bleeding event occurs, the Investigator or designee should notify the Medical Monitor (or designee) and additional testing of coagulation parameters (activated partial thromboplastin time [aPTT], prothrombin time [PT], INR), PLT count, and PLT volume may be performed.

Major bleeding is defined as one of the following (Schulman and Kearon 2005):

- 1. Fatal bleeding
- 2. Symptomatic bleeding in a critical area or organ, such as intracranial, intraspinal, intraocular, retroperitoneal, intraarticular if in a major joint, or pericardial, or intramuscular with compartment syndrome
- 3. Clinically overt bleeding leading to transfusion of ≥ 2 units of packed RBCs or whole blood or a fall in Hb of 20 g/L (1.24 mmol/L) or more within 24 hours

Clinically relevant non-major bleeding is defined as any sign or symptom of hemorrhage (e.g. more bleeding that would be expected for a clinical circumstance, including bleeding found by imaging alone) that does not fit the criteria for MB but does meet at least one of the following criteria (Kaatz et al. 2015):

- 1. Requiring medical intervention by a healthcare professional
- 2. Leading to hospitalization or increased level of care
- 3. Prompting a face to face (i.e., not just a telephone or electronic communication) evaluation

Minor bleeding events are those that do not fulfill the criteria for MB or CRNMBs (defined above), for example excess bruising, petechiae, gingival bleeding on brushing teeth.

8.6. Stopping Rules

Monitoring rules are described above in Section 8.5.

For the purposes of the stopping rules, Baseline is defined as the average of the pre-dose Study Day 1 value and the last value prior to Study Day 1.

8.6.1. Stopping Rules for Liver Chemistry Elevations

In the event of laboratory results meeting the following criteria, and the event is without an alternative explanation as discussed with the Sponsor Medical Monitor, dosing of a patient with Study Drug (ISIS 721744 or placebo) will be stopped permanently; values that are not confirmed due to failure to retest or missing lab values will be presumed confirmed:

- 1. ALT or AST $> 8 \times ULN$, which is confirmed
- 2. ALT or AST > $5 \times ULN$, which is confirmed and persists for ≥ 2 weeks
- 3. ALT or AST > $3 \times ULN$ (or the greater of 2 x baseline value or $3 \times ULN$ if the baseline value was > ULN), which is confirmed **and** total bilirubin > $1.5 \times ULN$ or INR > 1.5
- 4. ALT or AST > 3 × ULN (or the greater of 2 x baseline value or 3 x ULN if the baseline value was > ULN), which is confirmed, **and** the new appearance (i.e., onset coincides with the changes in hepatic enzymes) of fatigue, nausea, vomiting, right upper quadrant pain or tenderness, fever, rash, and/or concomitant eosinophilia (> ULN)

8.6.2. Temporary Stopping Rules for Renal Function Test Results

In the event of a persistent elevation that is observed over 2 consecutive weeks, for either of the 2 criteria below, dosing of a patient with Study Drug (ISIS 721744 or placebo) may be stopped temporarily:

- Serum creatinine increase that fulfills all of the following criteria: ≥ 0.3 mg/dL (26.5 μmol/L) and ≥ 40% above baseline creatinine values and > ULN (refer to definition of Baseline in Section 8.6)
- 2. UPCR >1000 mg/g, confirmed by a quantitative total urine protein measurement of > 1.0 g/24 hours

The possible dosing re-initiation or follow-up schedule for any events meeting either of these criteria will be determined by the Investigator or designee **in consultation with** the Sponsor Medical Monitor or designee.

8.6.3. Stopping Rules for Platelet Count Results

Actions to be taken in the event of a low PLT count are summarized in Table 2 above.

8.6.4. Stopping Rules for Bleeding Events

In the event of MB or CRNMB (see definitions in Section 8.5.4 as assessed by the Investigator or designee, dosing of a patient with Study Drug (ISIS 721744 or placebo) may be stopped permanently. The follow-up schedule for any events meeting this stopping criterion will be determined, including the suitability of the patient for resumption of dosing by the Investigator or designee in consultation with the Medical Monitor (or designee).

8.7. Adjustment of Dose and/or Treatment Schedule

Down-titration of Study Drug (ISIS 721744 or placebo) will not be allowed during the study. Dose adjustments for PLT count reduction must be made in accordance with Table 2.

Other adjustments, including dose interruptions, will be allowed for safety or tolerability after consultation with the Sponsor Medical Monitor.

8.8. Discontinuation of Study Drug/Treatment

A patient must permanently discontinue study treatment for any of the following:

- The patient becomes pregnant. Report the pregnancy according to instructions in Section 9.5.4
- The patient withdraws consent or assent
- The patient withdraws from treatment (but does not withdraw consent or assent)
- The patient experiences an AE that necessitates permanent discontinuation of Study Drug
- The patient develops laboratory test abnormalities that meet any of the stopping rules listed in Section 8.6
- The patient experiences an AE that necessitates unblinding of the Investigator or designee or Sponsor to the patient's treatment assignment

The reason for discontinuation of Study Drug must be recorded in the eCRF and source documentation.

Patients who discontinue Study Drug will remain in the study and attend the Tx-ET Visit (Week 25 visit assessments), unless consent or assent is withdrawn. Any patient who discontinues early from the Treatment Period should be strongly encouraged to complete the Post-Treatment Period study visits, procedures and observations (see Appendix A).

8.8.1. Follow-up Visits for Early Termination from Treatment Period or Post-Treatment Period

If a patient discontinues early from the Treatment Period, Treatment Early Termination (Tx-ET) visit assessments should be performed 28 days from the last dose of Study Drug, and patients should start the 13 weeks Post-Treatment Period to collect the study assessments in accordance with the Schedule of Procedures in Appendix A. Patients should also be strongly encouraged to attend the landmark visit at Week 25 if they discontinue prior to Week 25 to collect HAE attacks and conduct safety assessments in accordance with Appendix A. Depending on the day of discontinuation, Post-Treatment visits and the landmark visit may overlap and can be combined.

Any patient who chooses to discontinue early from the Post-Treatment Period should be strongly encouraged to complete safety procedures and observations in accordance with Appendix A. If the patient declines or is unable to participate in the above, final Post-Treatment Early Termination (Post-Tx ET) assessments should be performed at the time of withdrawal in accordance with Appendix A.

Amendment 2 12 July 2022

8.8.2. Temporary Pause/Safety Review

The trial should be halted for a safety review based on the following criteria:

- Death in any subject in which the cause of death is judged to be probably or definitely related to the study drug by the treating investigator
- The occurrence in any subject of a life-threatening SAE that is assessed to be related to the study drug by the treating investigator
- Two occurrences of Grade 3 or higher toxicities that are assessed to be related to the study drug by the treating investigator
- Two occurrences of a clinically significant Grade 3 or higher laboratory abnormality assessed to be related to the study drug by the treating investigator

8.9. Withdrawal of Patients from the Study Procedures

Patients must be withdrawn from study procedures for any of the following:

- Withdrawal of consent or assent
- The patient is unwilling or unable to comply with the protocol
- The patient meets any of the Exclusion Criteria (see Section 5.2) after enrolling in the study that in the opinion of the Investigator represents a safety risk to the patient

Other reasons for withdrawal of patients from the study may include the following:

- At the discretion of the Investigator or designee for medical reasons
- At the discretion of the Investigator or designee or Sponsor for non-compliance
- Significant protocol deviation

All efforts will be made to complete and report the observations as thoroughly as possible up to the date of withdrawal. All information, including the reason for withdrawal from study, must be recorded in the eCRF.

Any patient who withdraws consent or assent to participate in the study will be removed from further treatment and study observation immediately upon the date of request. These patients should be encouraged to complete the respective ET study procedures (Week 25 or Post-Treatment Week 13 visit assessments) and observations at the time of withdrawal (see Appendix A).

For patients withdrawn for reasons other than withdrawal of consent or assent, every effort should be made to complete the ET study procedures and observations at the time of withdrawal (see Appendix A) and ideally within 4 weeks from the last dose of Study Drug.

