8.5.3. Safety Monitoring Rules for Platelet Count Results

Platelet count will be monitored at least every 4 weeks during the Treatment and Post-Treatment Periods as per visit schedule in Appendix A.

The Investigator or the designee should review all PLT count results within 48 hours of receipt. Any unreportable PLT count result must be rechecked ideally within 7 days and determined not to have met a stopping rule before dosing can continue.

Actions to be taken in the event of reduced PLT count are shown in Table 2.

Protocol

Platelet count (K/mm³)	Dosing	Monitoring frequency
≥ 125	No action	At least every 4 weeks.
> 100 to < 125	Dosing every 4 (Cohort A) or 8 (Cohort B) weeks should be continued.	At least every 2 weeks until 2 successive values > 125K/mm ³ .
$\geq 75 \text{ to} \leq 100$	Dosing every 4 (Cohort A) or 8 (Cohort B) weeks may be continued if approved by the Sponsor Medical Monitor.	Every week until 2 successive values > 100K/mm³. Consider more frequent monitoring if additional risk factors for bleeding are present.*
≥ 50 to < 75	Pause dosing. When PLT count returns to > 100K/mm ³ , restart dosing only if approved by the Sponsor Medical Monitor.	Twice weekly until 2 successive values > 75K/mm³, then weekly until 2 successive values > 100K/mm³. Consider more frequent monitoring if additional risk factors for bleeding are present.*
≥ 25 to < 50	Permanently discontinue Study Drug. Consider corticosteroids if additional risk factors for bleeding are present.**	Twice weekly until 2 successive values > 75K/mm³, then weekly until 2 successive values > 100/mm9. Consider more frequent monitoring if additional risk factors for bleeding are present.*
< 25	Permanently discontinue Study Drug. Corticosteroids strongly recommended.**	Daily until 2 successive values > 25K/mm³, then twice weekly until 2 successive values > 75K/mm³, then weekly until 2 successive values > 100K/mm³. Consider more frequent monitoring if additional risk factors for bleeding are present.*

^{*} The suitability of the patient for interrupted and/or continued dosing will be determined by the Investigator or designee in consultation with the Medical Monitor and will be based on factors such as the original rate of decline in the patient's PLT count, whether any bleeding events were experienced by the patient, and the speed of recovery of PLT count after interruption of dosing.

There will be lab alerts for PLT values under 100,000/mm³.

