3.2. Study Estimand and Endpoints

3.2.1. Intercurrent events

The following intercurrent events will be considered when define estimand:

- 1. Treatments are early terminated, e.g.
 - a. Patients escaping early to the OLE study due to experiencing ≥ 5 recurrent HAE attacks per month for 2 consecutive months during the Treatment Period;
 - b. Patients discontinuing the study treatment early due to recurrent HAE attacks and not enrolling in the OLE study;
 - c. Patients discontinuing the study treatment early due to COVID-19 or war-related events.
- 2. Not allowed concomitant therapy or procedures defined in the Protocol Section 8.10 are used.

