3.2.2. Estimand and Main Estimator/Primary Endpoint for the Primary Objective

The estimand for the primary objective is to evaluate the difference between randomized study medication of ISIS 721744 80 mg once every 4 weeks and Placebo in the Investigator-confirmed HAE attack count from Week 1 to Week 25 irrespective of intercurrent events on the Full Analysis Set (FAS).

The main estimator, i.e. primary endpoint is the time-normalized number of Investigator-confirmed HAE attacks (per every-4-week) from Week 1 to Week 25 compared to placebo.

Investigator-confirmed HAE attacks will be continuously collected until Week 25 no matter which intercurrent event is occurred. The primary analysis will be performed based on the treatment policy strategy.

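### Section 8.9 takes consenting patients out of study procedures without carrying over attack collection to Week 25, which the SAP's treatment-policy estimand requires; the likely bias is small and the fix cheap.

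*Combined protocol and SAP*

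**What the plan says.** Protocol Section 8.9 has two tiers.

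- **Mandatory.** "Patients must be withdrawn from study procedures for any of the following". Three reasons are then listed. One is that consent or assent has been revoked. Another reads "The patient is unwilling or unable to comply with the protocol". The last is an exclusion criterion met after enrolling, if the investigator considers it a safety risk.
- **Permitted.** Withdrawal from the study for medical reasons; "At the discretion of the Investigator or designee or Sponsor for non-compliance"; or "Significant protocol deviation".

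For withdrawals other than consent, 8.9 asks for observations up to the withdrawal date and every effort to complete the early-termination procedures, ideally within 4 weeks of the last dose. It asks for nothing later.

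Stopping drug is treated differently. Section 8.8: "Patients who discontinue Study Drug will remain in the study and attend the Tx-ET Visit", unless consent is withdrawn. Section 8.8.1 adds the 13-week post-treatment period and strongly encourages a Week 25 landmark visit to collect attacks.

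SAP Section 3.2.1 lists among the intercurrent events: "Not allowed concomitant therapy or procedures defined in the Protocol Section 8.10 are used". SAP Section 3.2.2 then says: "Investigator-confirmed HAE attacks will be continuously collected until Week 25 no matter which intercurrent event is occurred", and adopts a treatment-policy strategy. SAP Section 4.1 repeats that data collection continues after any intercurrent event.

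**The concern.** A treatment-policy analysis needs attacks observed after the intercurrent event. Use of disallowed therapy is a named intercurrent event, and it also breaches protocol Section 8.10, so a site or the sponsor may handle it under 8.9 as non-compliance or a significant deviation. In that case the protocol allows observation to end at the point from which the SAP wants it to continue. A patient judged unable to comply must leave study procedures even if willing to answer the weekly attack call.

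Such removals happen after randomisation and may depend on disease course, because poorly controlled patients have the most reason to add prophylaxis. The primary model uses log observation time as offset, so it in effect carries the pre-removal rate forward. For a placebo patient who switches to effective prophylaxis, the high rate is kept and the low one is never seen, which favours the drug. For an active patient removed and no longer dosed, the low rate is kept, which also favours the drug.

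**Working it through.** **Plan's own figure.** Protocol 10.2 claims at least 90% power with 54 patients (36:18), 1.38 versus 13.26 attacks per 6 months, two-sided 0.05. The standard error of the log rate ratio is √(1/(36×1.38) + 1/(18×13.26)) = √(0.02013 + 0.00419) = 0.156. With ln(13.26/1.38) = 2.263, z is about 14.5 and power about 100%. A simulation with Pearson scaling agrees. Power is not affected by this point.

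**Do the texts conflict?**

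| | Stops drug (8.8, 8.8.1) | Withdrawn, consent intact (8.9) | SAP 3.2.2 needs |
|---|---|---|---|
| Early-termination assessment | yes | best effort | – |
| Week 25 landmark visit | strongly encouraged | not mentioned | attacks to Week 25 |
| Post-treatment follow-up | 13 weeks | not mentioned | – |

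Under SAP 4.9.1.3, attacks are missing when the study termination date falls before 24 weeks, so an 8.9 withdrawal creates missing primary data directly.

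**Size, placebo direction.** From the documents: 21 pooled placebo patients, 13.26 attacks per 6 months. Assumptions: six 4-week periods (2.21 per period); *k* patients removed after two periods at pre-switch rate *r*; true rate after the switch 0.5 per 4 weeks; simple pooled rates without the baseline covariate.

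- Analysed rate = [(21−k)×13.26 + 2kr] / [6(21−k) + 2k]
- Treatment-policy rate = [(21−k)×13.26 + k(2r + 4×0.5)] / 126

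With r = 4, and the planned active rate 1.38/6 = 0.23:

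| k | Analysed | Treatment policy | Excess | Reduction, analysed | Reduction, treatment policy |
|---|---|---|---|---|---|
| 1 | 273.20/122 = 2.239 | 275.20/126 = 2.184 | 2.5% | 89.7% | 89.5% |
| 2 | 267.94/118 = 2.271 | 271.94/126 = 2.158 | 5.2% | 89.9% | 89.3% |
| 3 | 262.68/114 = 2.304 | 268.68/126 = 2.132 | 8.1% | 90.0% | 89.2% |

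Reduction = 1 − 0.23/rate. The excess barely moves for r between 2.2 and 5 (k = 2: 5.2% throughout). With the lay summary's active rate of 0.44 instead, k = 3 gives 1 − 0.44/2.304 = 80.9% against 1 − 0.44/2.132 = 79.4%, so 1.5 points.

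**Size, active direction.** Assume *d* of 42 active patients leave at week 12 and have the full placebo rate from then on. The offset ratio stays at 1.38/13.26 = 0.104. The full-period ratio is 0.104×(1 − d/84) + d/84, which gives 0.115, 0.125, 0.147 and 0.189 for d = 1, 2, 4 and 8. At the lay-summary rates (0.44 versus 2.26, 45 active), 0.195 becomes 0.204 to 0.266. An immediate return to the placebo rate is a harsh assumption, given the half-life of about 4 to 5 weeks in protocol 2.4. The conclusion does not reverse anywhere in this range.

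**The case against.** Four stronger readings are tempting; the documents support none of them in full.

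*A reader might infer that 8.9 removes every patient with a deviation or a disallowed drug.* It does not. Those reasons are permissive, and Section 8.10 only requires concomitant therapy to be recorded. The placebo scenario above therefore rests on a permission being used. What stands is that nothing in 8.9 tells a site to keep collecting attacks when it uses that permission, and two reasons other than consent are mandatory.

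*A reader might infer that a laboratory value alone forces a patient out.* Platelets below 130 K/mm³ and ALT or AST above 3 × ULN are exclusion criteria, while 8.5.1 requires retesting and Table 2 says, at >100 to <125 K/mm³, "Dosing every 4 (Cohort A) or 8 (Cohort B) weeks should be continued". But exclusion criterion 4 concerns screening values, and the 8.9 bullet also needs an investigator judgement of safety risk. The overlap is an ambiguity to reconcile, not a demonstrated contradiction.

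*A reader might infer that safety data stop.* Sections 9.4.1, 9.4.3.6 and 9.5.1 continue follow-up of serious events, events of special interest and clinically significant laboratory abnormalities. What lapses is the scheduled visits.

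*A reader might infer that the SAP has no answer to the missing data.* It plans jump-to-reference imputation, which addresses the active direction, and a two-way tipping-point analysis that takes the placebo rate down towards zero, which covers the placebo direction. This largely stands as a defence of robustness. Its limits are that jump-to-reference imputes placebo gaps at the pooled placebo rate, so it cannot show a fall after a switch; the tipping-point range is chosen after unblinding (SAP 4.9.2.5); and imputation does not supply the observations that the estimand calls for.

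**Conclusion.** The point holds as a conflict over data collection. Section 8.9 ends observation for some consenting patients, by requirement or by discretion, while SAP 3.2.2 promises attacks to Week 25 regardless. The resulting gaps are avoidable and possibly informative, and the primary analysis treats them as missing at random.

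The likely size is modest. One to three placebo removals out of 21 raise the analysed placebo rate by about 2.5% to 8%, under one percentage point of the estimated reduction at planning rates. This depends on the assumed number of removals, switch time and post-switch rate; the documents give no count of 8.9 withdrawals. Active-arm removals could move the ratio further under the harsher assumption shown, but jump-to-reference is aimed at that case. A reader might infer that the primary result is in doubt; these figures do not support that. This is a cheap improvement, not a threat to the conclusion.

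**What to change.** State in 8.9 that, unless consent or assent is withdrawn or the patient is lost to follow-up, attack collection (the existing weekly contacts and the Week 25 landmark visit) and safety follow-up continue as in 8.8.1. Report all 8.9 withdrawals by arm, reason and timing; this can be done even when follow-up is already complete.

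The sponsor should also reconcile the exclusion-criterion bullet in 8.9 with 8.5, Table 2 and 8.8, so that the sections do not point to different actions for the same finding. Which clinical rule applies is for the sponsor. Moving the 8.9 reasons into 8.8 is not suggested: that list is of mandatory permanent discontinuations, so discretionary reasons would become compulsory stops of study drug.

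Cost: protocol wording, a site memo and one disposition table. Some non-compliant patients would stay on weekly calls, and a patient unwilling to comply may decline them. Their attacks may slightly dilute the estimate, although a treatment-policy estimand is meant to include them.

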8.10. Concomitant Therapy and Procedures

The use of concomitant therapies or procedures defined below must be recorded on the patient's eCRF. Adverse events related to administration of these therapies or procedures must also be documented on the appropriate eCRF.

8.10.1. Concomitant Therapy

A concomitant therapy is any non-protocol-specified drug or substance (including over-the-counter medications, herbal medications, and vitamin supplements) administered between Screening and the end of the Post-Treatment Period.

Allowed Concomitant Therapy

During the course of the study, the use of acute HAE medications (plasma-derived or recombinant C1-INH concentrate, BK2-receptor antagonist, or kallikrein inhibitor) to treat angioedema attacks is allowed as medically indicated. Patients can be treated with on-demand therapy as determined by their treating physician.

All other stable medications (if not excluded below) are allowed, so long as the dose and type is not expected to change during the study.

Disallowed Concomitant Therapy

1. Chronic prophylaxis for angioedema attacks, except for a stable dose of androgens or tranexamic acid. Any chronic use of other HAE prophylactic agents such as lanadelumab or berotralstat will not be permitted during the Treatment Period.

NOTE: The use of acute HAE medications (plasma-derived or recombinant C1-INH concentrate, BK2-receptor antagonist, or kallikrein inhibitor) to treat angioedema attacks is allowed as medically indicated

- 2. ACE inhibitors or any estrogen-containing medications with systemic absorption (such as oral contraceptive or hormonal replacement therapy)
- 3. Any oligonucleotides (including siRNA) other than ISIS 721744
- 4. Any other investigational drug or device

Patients should consult with the Investigator or designee prior to initiating any new medication, including non-prescription or herbal compounds or any non-drug therapy.

